## LIST OF ABBREVIATIONS

AE	Adverse event
ALT	Alanine aminotransferase
AML	Acute Myeloid Leukemia
ANC	Absolute neutrophil count
aPTT	Activated partial thromboplastin time
AST	Aspartate aminotransferase
CBC	Complete blood count
CML	Chronic Myelogenous Leukemia
CMML	Chronic Myelomonocytic Leukemia
CMP	Comprehensive metabolic panel
CNS	Central Nervous System
CR	Complete Remission
CrCl	Creatinine clearance
CRF	Case Report Form
CRi	Complete Remission with incomplete recovery
CTCAE	Common Terminology Criteria for Adverse Events
DLT	Dose limiting toxicity
DSMB	Data and Safety Monitoring Board
ECG	Electrocardiogram
ECHO	Echocardiogram
ECOG	Eastern Cooperative Oncology Group
EFS	Event-free survival
ET	Essential Thrombocythemia
FDA	Food and Drug Administration
FISH	Fluorescence in situ hybridization
GCP	Good Clinical Practice
GFR	Glomerulus filtration rate
GI	Gastrointestinal
HCG	Human chorionic gonadotropin
Hgb	Hemoglobin
HIPAA	Health Insurance Portability and Accountability Act
HIV	Human Immunodeficiency virus
HSCT	Hematopoietic Stem Cell Transplantation
ICF	Informed consent form
INR	International normalized ratio
IRB	Institutional Review Board
LAIP	Leukemia-associated immunophenotypes
LDAC	Low dose cytarabine

LDH	Lactate dehydrogenase
LSC	Leukemic stem cells
LVEF	Left Ventricular Ejection Fraction
MDS	Myelodysplastic Syndrome
MFC	Multiparameter flow cytometry
MPN	Myeloproliferative Neoplasm
MRD	Minimal/Measurable Residual Disease
NCI	National Cancer Institute
NGS	Next Generation Sequencing
NYHA	New York Heart Association
ORR	Overall response rate
OS	Overall survival
PI	Principal investigator
Plt	Platelet
PO	per os/by mouth/orally
PT	Prothrombin time
PV	Polycythemia Vera
RFS	Relapse-free survival
RSC	Radiation Safety Committee
RT-PCR	Reverse transcription polymerase chain reaction
SAE	Serious adverse event
SGOT	Serum Glutamic Oxaloacetic Transaminase
SMO	Smoothened
SPGT	Serum Glutamic Pyruvic Transaminase
Sub-I	Sub-investigator
ULN	Upper limit of normal
UPR	Unanticipated problem
WBC	White blood cell
WHO	World Health Organization

**STUDY SCHEMA**

\*Treatment will be discontinued for induction failure, relapsed or progressed disease, treatment intolerance, continuation to HSCT or at any point based on the investigator's discretion. At discontinuation, subjects will enter the follow-up portion of the study.

**STUDY SUMMARY**

Title	Phase II study of the combination of CPX-351 and Glasdegib in previously untreated patients with Acute Myelogenous Leukemia with MDS related changes or therapy-related Acute myeloid leukemia: A University of California Hematologic Malignancies Consortium Protocol (UCHMC1913/UCI 18-105)
Short Title	CPX-351 and Glasdegib for newly diagnosed acute myelogenous leukemia with MDS related changes or therapy-related Acute myeloid leukemia
Phase	Phase 2
Sponsor	University of California Hematologic Malignancies Consortium
Methodology	Single-arm, open-label trial
Study Duration	2-3 years
Study Center(s)	The University of California Hematologic Malignancies Consortium: University of California, Irvine University of California, Los Angeles University of California, San Diego University of California, San Francisco University of California, Davis
Objectives	
Primary objective:
 
 
Determine the efficacy of the combination of CPX-351 and Glasdegib for newly diagnosed AML with MDS related changes and therapy-related AML
 
 
Secondary objectives:
 
 
Determine the toxicity of the combination of CPX-351 and Glasdegib in adults with newly diagnosed AML with MDS related changes
 
Determine the rate of response by measuring overall remission rate (ORR) of the combination. The overall remission rate includes complete remission (CR) and complete remission with incomplete recovery (CRi)
 
Determine the durability of response by measuring relapse free survival (RFS)
 
Determine the survival and length of survival by measuring Overall Survival (OS)
 
Determine the time to return of normal hematopoiesis, duration of response
 
Determine the proportion of patients who go on to receive allogeneic HSCT
 
 
Exploratory objectives:
 
 
Determine if MRD status based on multiparameter flow cytometry from University of Washington can be used as a surrogate marker for survival
 
To determine if gene expression profiling can be biomarkers of response
 

Number of Subjects	30 evaluable subjects
Diagnosis and Main Inclusion Criteria	1. Previously untreated therapy-related AML or AML with myelodysplastic related changes as described by WHO

	
2016
 
 
a. AML arising in MDS (including CMML) or MDS/MPN syndrome
 
b. AML with MDS-related cytogenetic abnormalities (Appendix A, metaphase FISH allowable as surrogate for cytogenetics)
 
c. AML with multilineage dysplasia involving the presence of 50% or more dysplastic cells in at least two cell lines and in the absence of mutation in NPM1 or biallelic CEBPA (as per WHO 2016)
 
 
 
2. Adults 18 years of age or older
 
3. ECOG performance status 0 to 2
 
4. Adequate organ function as defined as:             
 
a. Left Ventricular Ejection Fraction (LVEF) > 50%
 
b. Serum total bilirubin < 2.0 mg/dL, unless considered due to Gilbert's disease or leukemic involvement
 
c. AST, ALT and alkaline phosphatase < 3 times the upper limit of normal, unless considered due to leukemic involvement
 
d. Serum creatinine < 2.0 mg/dL, or creatinine clearance > 40 mL/min based on Cockcroft-Gault GFR
 
 
 
5. Absence of unstable cardiac disease defined as myocardial infarction within 6 months, uncontrolled heart failure, or uncontrolled cardiac arrhythmia
 
6. Ability to understand and the willingness to sign a written informed consent or subject's legally authorized representative (LAR) has provided informed consent prior to any study-specific activities/procedures being initiated when the subject has any kind of condition that, in the opinion of the investigator, may compromise the ability of the subject to give written informed consent
 
7. Women of child-bearing potential and men with partners of child-bearing potential must agree to use 2 methods of birth control or be surgically sterile, or abstain from heterosexual activity for the course of the study through 120 days after the last dose of study medication
 
 
A woman of child-bearing potential is any female (regardless of sexual orientation, having undergone a tubal ligation, or remaining celibate by choice) who meets the following criteria:
 
 
• Has not undergone a hysterectomy or bilateral oophorectomy; or
 
• Has not been naturally postmenopausal for at least 12 consecutive months (i.e., has had menses at any time in
 

--	--

	
the preceding 12 consecutive months)
 
Women of child-bearing potential has negative pregnancy test within 72 hours of initiating study drug dosing
 
Male subjects must agree to use a latex condom during sexual contact with females of childbearing potential even if they have had a successful vasectomy starting with the first dose of study therapy through 120 days after the last dose of study therapy
 
8. Leukapheresis, corticosteroid and hydroxyurea are permitted as initial management of hyperleukocytosis at the investigator's discretion for up to 7 days after starting study therapy. Hyperleukocytosis is defined as greater than 30k WBC. When possible, a bone marrow biopsy for screening should be performed prior to the initiation hyperleukocytosis management

Exclusion Criteria
	
 
1. Prior treatment with Glasdegib or CPX-351
 
2. Previously treated AML except for initial management of hyperleukocytosis. Treatment with hypomethylating therapy for MDS is allowable but not since their diagnosis of AML. No prior treatment with cytarabine or daunorubicin are allowed
 
3. Concurrent FLT3 mutation that the treating physician deems necessary to treat with midostaurin, whereas patients with FLT3-mutated AML not treated with midostaurin can be enrolled. Patients with known Core Binding Factor -t(8;21), inv(16), t(16;16) are allowed for study participation at the treating investigator's discretion
 
4. Active CNS or testicular involvement by leukemia; diagnostic lumbar puncture is not required
 
5. History of neurologic disorder including but not limited to: prior seizure, epilepsy, structural brain abnormality, benign brain tumor, stroke, brain injuries, dementia, movement disorder or other significant CNS abnormalities
 
6. Baseline QT corrected interval based on Fridericia's formula (QTcF) interval > 450 ms
 
7. Acute coronary syndrome in the past 12 months, NYHA class III or VI
 
8. Known history of Wilson's disease or other copper handling disorder
 

	
 
9. History of GI malabsorptive disease
 
10. Has a known additional malignancy that is progressing or requires active treatment. Exceptions include basal cell carcinoma of the skin, squamous cell carcinoma of the skin, or in situ cervical cancer that has undergone potentially curative therapy
 
11. Known HIV infection
 
12. Active hepatitis B or hepatitis C infection (patients who successfully completed curative hepatitis C therapy can be enrolled)
 
13. Any uncontrolled infection, active bacterial or viral infection manifesting as fevers or hemodynamic instability within the past 72 hours
 
14. Proven active invasive fungal infection
 
15. Is pregnant or breastfeeding, or expecting to conceive or father children within the projected duration of the trial, starting with the pre-screening or screening visit through 120 days after the last dose of trial treatment
 
16. Severe or uncontrolled medical disorder that would, in the investigator’s opinion, impair ability to receive study treatment (i.e., uncontrolled diabetes, chronic renal disease, chronic pulmonary disease or active, uncontrolled infection, psychiatric illness/social situations that would limit compliance with study requirements
 
17. Current or anticipated use of other investigational agents
 
18. For patients with prior anthracycline exposure, the cumulative life-time dose should not exceed 386mg/m^2 at the time of study entry (to convert different anthracycline to daunorubicin-equivalent, see Appendix H for conversion factors)
 

Study Product(s)	CPX-351 and Glasdegib
Duration of administration	
 
• CPX-351 will be administer during Induction on days 1, 3 and 5. Glasdegib will be given starting on day 6 and continuing until beginning of consolidation
 
• Consolidation can be either 1 or 2 cycles. CPX-351 will be administered during days 1 and 3. Glasdegib will begin on day 4 and continue daily
 
• If the patient is a candidate for HSCT and moves forward with HSCT, then Glasdegib will be discontinued at least 7 days prior
 

	
 
• During Maintenance, Glasdegib will be taken daily for up to 1 year
 

Reference therapy	Lancet Phase II CPX-351 versus 7+3. Blood 2014
Study Outcome Measures	
Safety
 
 
• Common Terminology Criteria for Adverse Events (CTCAE) version 5.0
 
• Adverse events
 
• Serious adverse events
 
• Adverse events leading to discontinuation of study therapy
 
 
Efficacy
 
 
• Event-free survival
 
• Objective response rate → complete remission (CR) plus complete remission with incomplete hematologic recovery (CRi)
 
• Relapse free survival
 
• Duration of response
 
• Time to return of normal hematopoiesis
 
• Overall survival
 
• Proportion of patients who go on to receive allogeneic HSCT
 
 
Exploratory outcome measures
 
 
• Determine if MRD status can be used as a surrogate marker for survival
 
• Determine if using gene expression profiling can identify subset of patients who are more likely to respond
 

Rationale	
In the phase III trial of CPX-351 versus 7+3 chemotherapy for first line treatment of secondary AML in patients 60-75 years of age, 309 patients were treated with either of the two regimen. There was a statistically significant improvement in overall survival as well as overall remission rate in the CPX-351 arm.
 
Glasdegib in combination with LDAC has been shown to have tolerable side effect profile while improving survival outcomes in some patients with elderly AML who are unfit for chemotherapy. In the phase II trial of Glasdegib with cytarabine and daunorubicin, 69 patients with newly diagnosed AML were treated with the combination. The overall survival of the combination was improved to historical controls.
 
We hypothesize that the combination of CPX-351 with Glasdegib will demonstrate improvements in event-free survival as well as being well tolerated.

**Study Title: Phase II study of the combination of Glasdegib and CPX-351 in previously untreated patients with Acute Myelogenous Leukemia with MDS related changes or therapy-related Acute myeloid leukemia: A University of California Hematologic Malignancies Consortium Protocol (UCHMC1913/UCI 18-105)**

**PI:** [name], Assistant Clinical Professor of Medicine

**Institution:** Chao Comprehensive Cancer Center, University of California Irvine, Orange, CA

UCHMC1913/UCI 18-105  

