## 3.0 PATIENT ELIGIBILITY

### 3.1 Inclusion Criteria

Subjects must meet all of the inclusion criteria to participate in this study.

1. Previously untreated therapy-related AML or AML with myelodysplastic related changes as described by WHO 2016
  - a. AML arising in MDS (including CMML) or MDS/MPN syndrome
  - b. AML with MDS-related cytogenetic abnormalities (Appendix A, metaphase FISH allowable as surrogate for cytogenetics)
  - c. AML with multi-lineage dysplasia involving the presence of 50% or more dysplastic cells in at least two cell lines and in the absence of mutation in NPM1 or biallelic CEBPA (as per WHO 2016)
2. Adults 18 years of age or older
3. ECOG performance status 0 to 2
4. Adequate organ function as defined as:
  - a. Left Ventricular Ejection Fraction (LVEF) > 50%
  - b. Serum total bilirubin < 2.0 mg/dL, unless considered due to Gilbert's disease or leukemic involvement
  - c. AST, ALT and alkaline phosphatase < 3 times the upper limit of normal, unless considered due to leukemic involvement
  - d. Serum creatinine < 2.0 mg/dL, or creatinine clearance > 40 mL/min based on Cockcroft-Gault GFR
5. Absence of unstable cardiac disease defined as myocardial infarction within 6 months, uncontrolled heart failure, or uncontrolled cardiac arrhythmia
6. Ability to understand and the willingness to sign a written informed consent or subject's legally authorized representative (LAR) has provided informed consent prior to any study-specific activities/procedures being initiated when the subject has any kind of condition that, in the opinion of the investigator, may compromise the ability of the subject to give written informed consent
7. Women of child-bearing potential and men with partners of child-bearing potential must agree to use 2 methods of birth control or be surgically sterile, or abstain from heterosexual activity for the course of the study through 120 days after the last dose of study medication

A woman of child-bearing potential is any female (regardless of sexual orientation, having undergone a tubal ligation, or remaining celibate by choice) who meets the following criteria:

- Has not undergone a hysterectomy or bilateral oophorectomy; or
- Has not been naturally postmenopausal for at least 12 consecutive months (i.e., has had menses at any time in the preceding 12 consecutive months)

Women of child-bearing potential has negative pregnancy test within 72 hours of initiating study drug dosing

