### 3.2 Exclusion Criteria

Subjects meeting any of the exclusion criteria at baseline will be excluded from study participation.

1. Prior treatment with Glasdegib or CPX-351
2. Previously treated AML except for initial management of hyperleukocytosis. Treatment with hypomethylating therapy for MDS is allowable but not since their diagnosis of AML. No prior treatment with cytarabine or daunorubicin are allowed
3. Concurrent *FLT3* mutation that the treating physician deems necessary to treat with midostaurin, whereas patients with *FLT3-mutated* AML not treated with midostaurin can be enrolled. Patients with known Core Binding Factor –t(8;21), inv(16), t(16;16) are allowed for study participation at the treating investigator's discretion
4. Active CNS or testicular involvement by leukemia; diagnostic lumbar puncture is not required
5. History of neurologic disorder including but not limited to: prior seizure, epilepsy, structural brain abnormality, benign brain tumor, stroke, brain injuries, dementia, movement disorder or other significant CNS abnormalities
6. Baseline QT corrected interval based on Fridericia's formula (QTcF) interval > 450 ms
7. Acute coronary syndrome in the past 12 months, NYHA class III or VI
8. Known history of Wilson's disease or other copper handling disorder
9. History of GI malabsorptive disease
10. Has a known additional malignancy that is progressing or requires active treatment. Exceptions include basal cell carcinoma of the skin, squamous cell carcinoma of the skin, or in situ cervical cancer that has undergone potentially curative therapy
11. Known HIV infection
12. Active hepatitis B or hepatitis C infection (patients who successfully completed curative hepatitis C therapy can be enrolled)
13. Any uncontrolled infection, active bacterial or viral infection manifesting as fevers or hemodynamic instability within the past 72 hours
14. Proven active invasive fungal infection
15. Is pregnant or breastfeeding, or expecting to conceive or father children within the projected duration of the trial, starting with the pre-screening or screening visit through

120 days after the last dose of trial treatment

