16. Severe or uncontrolled medical disorder that would, in the investigator's opinion, impair ability to receive study treatment (i.e., uncontrolled diabetes, chronic renal disease, chronic pulmonary disease or active, uncontrolled infection, psychiatric illness/social situations that would limit compliance with study requirements)
17. Current or anticipated use of other investigational agents
18. For patients with prior anthracycline exposure, the cumulative life-time dose should not exceed 386mg/m^2 at the time of study entry (to convert different anthracycline to daunorubicin-equivalent, see [Appendix H](#) for conversion factors)

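### Exclusion 7 names NYHA class III and a class VI that does not exist, in all three places where it is printed, so it does not name class IV

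*Combined protocol and SAP*

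**What the plan says.** Exclusion 7 reads "Acute coronary syndrome in the past 12 months, NYHA class III or VI". The wording is identical in the Study Summary, in Section 3.2 and in the Appendix G eligibility checklist. The List of Abbreviations expands NYHA as "New York Heart Association", but no section defines the classes and no criterion mentions class IV.

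Other criteria bear on the same patients:

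- Inclusion 5 requires "Absence of unstable cardiac disease defined as myocardial infarction within 6 months, uncontrolled heart failure, or uncontrolled cardiac arrhythmia".
- Inclusion 4a requires "Left Ventricular Ejection Fraction (LVEF) > 50" per cent, with an echocardiogram at screening (Section 7.1.12).
- Inclusion 3 limits ECOG performance status to 0 to 2.
- Exclusion 16 begins "Severe or uncontrolled medical disorder that would" and turns on the investigator's opinion that the disorder would impair the ability to receive treatment.

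The lists combine by two stated rules. Section 3.1 says "Subjects must meet all of the inclusion criteria to participate in this study", and Section 3.2 says "Subjects meeting any of the exclusion criteria at baseline will be excluded from study participation". Sections 4.2 and 7.1.4 add a central step: the initiating site's principal investigator and research manager review the signed checklist and source documents before treatment starts.

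**The concern.** A class-based exclusion is meant to give every site the same threshold. This one pairs class III with a class that is not on the scale. The anomaly shows in the line itself, which jumps from III to VI and passes over the numbers between them. On a literal reading the criterion excludes the less severe of the two symptomatic classes one would expect it to cover and is silent on the more severe one.

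The line is a cardiac safety screen ahead of an anthracycline-containing regimen. Section 1.5.2 lists congestive heart failure among the dose-limiting toxicities of CPX-351 in its first trial, at 134 units/m², a level that was then reduced. The trial may run at one to five centres (Section 13.1), and the checklist carrying the error is the form on which eligibility is signed and confirmed. A class IV patient could be entered without breaching any stated term of exclusion 7, and a monitor would have no printed class against which to raise a finding.

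**Working it through.** No formula applies. The check compares the texts and then applies the two combination rules.

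**1. Is it a single slip?** The Study Summary, Section 3.2 and Appendix G all give III or VI. Three of three copies agree, so it is neither an artefact of text extraction nor an error confined to the summary. No other section supplies a correction.

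**2. What does exclusion 7 name?** The scale has classes I, II, III and IV. This is general knowledge of a standard scale and is not stated in the protocol. Of the two classes printed, one exists (III) and one does not (VI). Class IV is not named.

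**3. Do the other criteria supply a class threshold?**

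| Provision | What it tests | Names an NYHA class? |
|---|---|---|
| Inclusion 5 | Heart failure that is uncontrolled (term not defined) | No |
| Inclusion 4a | Ejection fraction above 50% | No |
| Inclusion 3 with Appendix B | ECOG 0 to 2; grade 2 still means full self-care and more than half of waking hours out of bed | No |
| Exclusion 16 | Severe or uncontrolled disorder, in the investigator's opinion | No |
| Sections 4.2 and 7.1.4 | Central check of checklist, examination, ECOG, history, laboratory results and ECG | No |

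Each can stop a patient with severe heart failure, and together they would stop most. None restores the stated class limit. The list of documents in Section 7.1.4 does not include the echocardiogram report, although Section 4.2 does not limit the source that may be sent.

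**4. Do the coronary windows in exclusion 7 and inclusion 5 contradict each other?** Treat an infarction as one form of acute coronary syndrome, and read exclusion 7 as two separate bars, one coronary and one by class.

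| Event before entry | Infarction part of inclusion 5 | Coronary part of exclusion 7 | Result |
|---|---|---|---|
| Infarction, 0 to 6 months | Fails | Meets exclusion | Excluded |
| Infarction, 6 to 12 months | Passes | Meets exclusion | Excluded |
| Other acute coronary syndrome, 0 to 12 months | Not addressed | Meets exclusion | Excluded |
| Either, beyond 12 months | Passes | Not met | Not barred by either window |

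Passing an inclusion criterion does not admit a patient who meets an exclusion. Every row has one answer: the 12-month window decides and the 6-month one is redundant.

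**The case against.** The strongest reply is that this is a slip in a numeral whose intent anyone can see. An investigator who reads that class III is excluded together with some higher class would hardly conclude that class IV is welcome. A patient with heart failure of that severity would rarely have ECOG 0 to 2, would usually count as uncontrolled under inclusion 5 or as severe under exclusion 16, and would have to pass central review. This largely stands, and it is why the practical effect is rated small. It does not remove the error. The sponsor wrote a class threshold in addition to those bars, and the printed threshold is wrong on the form that sites sign.

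Three stronger readings are tempting, and the documents do not support them.

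- A reader might infer that class IV patients are eligible for the trial, or that only inclusion 5 stands in their way. The silence is that of exclusion 7 alone; the other provisions apply as well.
- A reader might infer that the 6-month and 12-month windows conflict. They cover different terms and sit in lists that apply together, so both can be followed. The comma in exclusion 7 leaves some room to read the NYHA class as qualifying the coronary event, but nothing in the documents shows that this was meant.
- A reader might gauge the stake by the planned daunorubicin exposure. From Section 5.1 this is 44 × 3 = 132 for induction, 44 × 2 = 88 for re-induction and 29 × 2 × 2 = 116 for two consolidation cycles, or 336 mg/m² if every cycle is given. The sum is right, but it does not measure any effect of the misprint. Likewise, no figure in the documents shows that the toxicity endpoint would be distorted by pre-existing cardiac disease.

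**Conclusion.** The point holds for the NYHA class. Exclusion 7 carries a wrong threshold in three of three places, and as printed one of its two classes does not exist and class IV is not named. The conclusion rests on one fact from outside the documents, that the scale ends at IV. The number of patients who could be affected cannot be derived from the protocol and is probably small, because four other criteria and central confirmation cover much of the same ground. What is lost is a uniform, checkable class limit in a cardiac safety screen.

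The coronary windows are a redundancy. The primary analysis of six-month event-free survival, its target of 30 evaluable participants and its power do not depend on this line.

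**What to change.** The sponsor should state the NYHA class or classes intended in exclusion 7 and make the same correction in the Study Summary, Section 3.2 and the Appendix G checklist. This review does not say which class should be excluded.

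As an optional clarification in the same amendment, the sponsor could print the coronary and NYHA parts of exclusion 7 as separate items and align the time windows of inclusion 5 and exclusion 7, or note that the longer one governs. The choice of window is the sponsor's.

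The cost is a one-line wording change in three places, IRB approval of the amendment, and a reissued checklist. Study procedures, sample size and analysis do not change.
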